15.4.3 Unanticipated Device Effect Reporting

All UADE/SADE/USADE **must be reported** to the Sponsor, via eCRF, **immediately upon awareness of event but no later than 72 hours** by the study site personnel. An investigator shall submit to the reviewing EC a report of any UADE occurring during an investigation according to EC requirements.

15.4.4 Events of Special Interest

All study device deficiencies must be reported to the Sponsor, via eCRF, as soon as possible, within 72 hours by the study site personnel. If a device failure is detected or suspected, it should be documented on the eCRF and the device returned according to the Sponsor's instructions.

The investigational device should be sent to appropriate R&D team or designated Quality engineer. Complaints related to non-investigational products manufactured and/or distributed by Biosense Webster, used during the procedure related to other devices (other than the study device under investigation), are to be reported according to current Biosense Webster procedures and other policies as necessary (i.e., institutional policies, EC policies, and

local regulations). Investigators are instructed to return devices in accordance with current company procedures and other relevant regulations.

Event reporting to relevant CAs in accordance with the jurisdictional regulations will occur by the sponsor and/or by the investigator, depending upon the local requirements and will be done in EU per MDR 2017/745.

A device deficiency related to a medical device not manufactured by Biosense Webster should be reported by the investigator to their respective manufacturer as per relevant regulation. Complaints related to non-Biosense Webster, Inc. products must be handled according to institutional policies, EC policies, and local regulations.

15.5 Safety Oversight

Safety oversight will be conducted as described in the Safety Management Plan. Aggregate safety data will be reviewed during enrollment by the study safety lead in order to promptly identify new issues or trends which may have an impact on the conduct of the study and/or subject safety. Under the rules of an approved study-specific charter, safety events will be reviewed by an established committee which may recommend appropriate action(s) to ensure subject safety.

16. Administrative Responsibilities

16.1 Ethics Committee and Competent Authority Application

The study protocol (or amendment[s]), ICF, and other applicable study related documents must be approved by the EC and CAs before enrollment of subjects. Any additional requirement imposed by the EC or CA shall be discussed, agreed upon, and followed. A signed copy of the EC and CA approval letters addressed to the investigator must be submitted to Biosense Webster certifying study approval prior to subject enrollment. Biosense Webster and the EC must approve, in writing, any changes to the protocol that affect the rights safety and/or welfare of the subjects or may adversely affect the validity of the study.

In addition, Biosense Webster, Inc. is responsible for notifying the relevant CA of the intention to perform a clinical investigation under this protocol and ensure to get the official response/approval before starting the clinical investigation.

16.2 Audits and Inspections

The sponsor and/or designee and/or CAs may contact the participating institution to inform the investigator of an upcoming audit/inspection. The investigator should immediately notify the sponsor of any CA audits/inspection at the study site. The audit/inspection can include the review of documents, facilities, records and any other resources deemed by the authorities to be related to study.

17. Deviations from the Clinical Study Plan

The investigator is responsible for ensuring that the clinical investigation is conducted in accordance with the procedures and evaluations described in this protocol. The study monitors shall verify that the conduct of the study is in compliance with the currently approved protocol and applicable regulations and shall identify any issues of non-compliance with regulations or guidelines.

Issues of non-compliance include but are not limited to repeated protocol deviations; failure to obtain proper informed consent; non-conformance to EC requirements; failure to report AEs, product malfunctions and other product issues; and other non-conformance to GCP.

A protocol deviation is defined as an instance of failure to follow, intentionally or unintentionally, the requirements of the protocol (e.g. missed test or procedure, visit out of window, non-adherence to inclusion/exclusion criteria). Investigators are not allowed to deviate from the protocol. Waivers are prohibited for this clinical study. Protocol deviations will be monitored closely and will be reported per EC/CA requirement.

Under emergency circumstances, deviations from the protocol to protect the rights, safety and well-being of a subject may proceed without prior approval of the sponsor and EC. Such deviations shall be documented and reported to the sponsor and the EC as required.

All instructions described in this study protocol are to be followed. If an amendment is required, it must be made in written form and receive approval from all persons and authorities who approved the original protocol. Administrative changes (do not affect subject's benefits/risks ratio) may be inserted with abbreviated approval. All amendments will be distributed to all original protocol recipients.

18. Investigational Product

18.1 Use of the Investigational Device and Investigator Experience

18.1.1 Training

The training of applicable clinical site personnel will be the responsibility of the Sponsor. Prior to initiating subject enrollment at a site, appropriate study training will be provided. Investigators selected to participate in the study will be experienced in intracardiac mapping and ablation.

To ensure uniform data collection and protocol compliance, the Sponsor will conduct a training session that will include reviewing the protocol, eCRF and data collection process, and the AE reporting process. The sponsor will reinforce the training or provide clarification throughout the study, as needed.

18.1.2 Materials

Biosense Webster, Inc. USA, is the legal manufacturer of the catheters to be used in this study. The investigational devices were built in a clean room environment, and sterilized using EtO gas, in a manner similar to standard, commercially approved Biosense Webster products. Further detail of catheter components coming into contact with the human body are described in the Investigator Brochure.

Complete manufacturing records of every lot of catheter manufactured for human use during this study are maintained at the respective manufacturing location. Each lot of catheters is released for human use under a Confirmation of Conformity from Regulatory Affairs that will certify that the investigational catheters conforms to the Essential Requirements for product release apart from those features, that are being investigated in this clinical investigation. And that, with regard to these aspects, every precaution has been taken to protect the health and safety of the patient.

18.2 Device Acquisition and Accountability

After obtaining a fully executed clinical trial agreement and appropriate CA/EC approvals, the study site will receive the necessary amount of study-related materials prior to commencement. Study-related devices (investigational and non-investigational) will be shipped to the site upon completion of required documentation. Investigational Study Devices will be labeled as “**Investigational Device**” and are only to be used for subjects enrolled in this clinical study.

The Sponsor will keep records of all investigational devices shipped to the site. Investigational site personnel are responsible for appropriate logging of devices received, verification of packing slip information (i.e. lot numbers and quantity shipped) and date and identifying that each device was used in the study and disposition information completed when returned to the Sponsor.

The Investigational Device Accountability Log shall record the following information:

- Date of receipt
- Person in receipt of the devices
- Quantity received
- Catalog number
- Serial/lot numbers
- Expiry Date
- Date device was used
- Subject ID on whom device was used
- Date of return
- Reason for return (i.e. used without incident, malfunction, expired, end of study, ...)

18.3 Device Returns

All investigational devices (**used and unused**) will be returned to the Sponsor’s attention and per Sponsor’s Instructions. Device deficiencies should be properly documented on the eCRF. Any suspected malfunctioning device or device associated with an AE (device related AE) will undergo a thorough complaint analysis. All returned devices must be properly labeled with the study name, the subject identification number, date of issue, identified as a defective return, non-defective return, or AE (as applicable). All tracking information must be retained in the event the package has been lost and requires tracking. All investigational devices should be returned.

19. Clinical Monitoring

Clinical site monitoring is conducted to ensure that the rights and well-being of human subjects are protected, that the reported trial data are accurate, complete, and verifiable, and that the conduct of the trial is in compliance with the currently approved protocol/amendment(s), with GCP, and with applicable regulatory requirement(s). Each site will undergo periodic monitoring of the study, which involves a visit from a Sponsor representative, qualified to perform such visit. Monitoring visits may include, but are not limited to, the following:

- Protocol adherence
- Source documentation verification and accuracy of the eCRFs

- Verification that informed consent is being obtained for all subjects participating in the study in accordance with requirements described in the study protocol
- Verification of completeness of the site file
- Verification of accuracy of all study logs such as the Delegation of Responsibility Log, etc.
- Compliance with applicable regulations
- Identification and action to resolve any issues or problems with the study.

Data are to be submitted promptly via e-CRF after collection. Missing or unclear data will be corrected as necessary throughout the trial. Biosense Webster will request further documentation such as physician and/or cardiac EP lab procedure notes when complications or malfunctions are observed and reported.

Further details on clinical monitoring are provided in the study specific monitoring plan.

20. Statistical Methodology

The Sponsor will be responsible for the overall analysis of data from this protocol. This section represents the Statistical Analysis Plan for this protocol. All analyses and subsequent detail are described below.

20.1 Levels of Significance

All data will be summarized by descriptive analyses. No formal statistical inference is planned. All confidence intervals will use the two-sided 95% confidence level unless otherwise stated.

20.2 Sample Size Justification

A sample size of 30 subjects will allow characterization of the performance and safety of the OPTRELL™ catheter. Approximately 20 atrial and 10 ventricular procedures will be performed.

The sample size of 30 patients was selected based on previous experience with similar design in first in human assessments of multi-electrode mapping catheters. This study is meant to characterize the catheter's ability to perform safely in various types of arrhythmias. No clinical claims of effectiveness or patient outcomes will be made from this study.

20.3 Analysis Sets

Safety Analysis Set : The Safety Analysis Set will consist of all enrolled subjects who have undergone insertion of the study catheter.

Per Protocol (PP) Analysis Set: The PP Analysis Set is a subset of the Safety Analysis Set and will include all enrolled subjects who meet the study eligibility criteria and in whom mapping procedures with the study catheter for the study arrhythmia are initiated.

20.4 Analyses to be conducted

20.4.1 General Conventions

Standard descriptive summaries for continuous data include the number of observations with data, mean, standard deviation (SD), median, minimum, and maximum values. The mean and median will be rounded to one decimal place greater than in the raw data where applicable; the standard deviation will be rounded to two decimal places greater than in the raw data where applicable. In cases where this is not applicable (e.g., average time spent), the mean will be rounded to one decimal place; the standard deviation to two decimal places; the minimum

and maximum to the nearest whole number. These will be referred to as “continuous summaries”.

For categorical data, the count and percent will be provided. Percentages will be based on the number of subjects without missing data. For adverse event and device effects data, percentages will be based on the number of subjects in the analysis population being used in the analysis. When count data are presented, the percentage for zero counts will be suppressed in order to draw attention to the non-zero counts. Frequency counts will be presented as whole numbers and percentages will be rounded to one decimal place. This will be referred to as “categorical summaries”.

Adverse Events (AE) tables will be sorted by decreasing frequency of events, unless otherwise specified.

20.4.2 Subgroups

Subjects will be enrolled into five arrhythmia subgroups:

Atrial procedures:

1. Scar-related Atrial Tachycardia
2. Persistent Atrial Fibrillation (PsAF)
3. Paroxysmal Atrial Fibrillation (PAF)

Ventricular procedures:

4. Ventricular Tachycardia (VT)
5. Premature Ventricular Complex (PVC)

20.4.3 Subject Disposition

Subject disposition will be summarized and listed for the subject categories defined in protocol section 10.3 for all subjects. Subject disposition will be summarized using categorical summaries. The number and percent of patients who were screened, enrolled in the study, failed inclusion/exclusion criteria, are included in the safety, and per-protocol analysis sets, completed the study, and prematurely discontinued from the study will be presented. Patients who are prematurely discontinued will be summarized by primary reason for discontinuation.

20.4.4 Demographic and Baseline Characteristics

Demographic variables will include age and sex. Baseline characteristics will include the primary study arrhythmia, duration of the primary arrhythmia since first onset, and average duration of arrhythmia episodes. The number of previous ablation procedures will be summarized by type of arrhythmia ablated, as well as the technology used in the most recent procedure. All demographic and baseline characteristics will be summarized using categorical and continuous summaries, as appropriate, for the Safety Analysis Set. A listing of subject demographic and baseline characteristics will be generated.

20.4.5 Medical History

Medical history will be presented using the Safety Analysis Set.

Cardiovascular (CV) and Thromboembolic/Cerebrovascular medical history will be collected and summarized using categorical summaries. Each subject will be counted once under each type of CV and/or thromboembolic/cerebrovascular medical history they have experienced.

The number of subjects with TTE performed and those with pericardial effusion will be presented using categorical summaries. The left ventricle ejection fraction, the LA diameter,

and the maximum dimension of pericardial effusion will be presented in continuous summaries. The number of subjects with an exam performed to assess the presence of thrombus will be listed with the type of exam performed and whether a thrombus was present.

Other medical history, including NYHA class, incidence of diabetes, and history of bleeding will be summarized similarly.

20.4.6 Procedural Data

General procedure data associated with the mapping and ablation will be summarized for the PP Analysis Set and includes the following parameters: the subjects heart rhythm at the start and end of the procedure and the duration of the procedure. The duration of the procedure will be presented along with the pre-ablation mapping time for each chamber being mapped.

The following elements of the pre-mapping index procedure success will be presented:

1. Whether the entire chamber and areas associated with the targeted arrhythmia(s) are completely mapped using fast anatomical mapping (FAM) (Y/N)
2. Whether the substrate or previous lesion line associated with the arrhythmia(s) is mapped (Y/N) along with type of mapping performed (as applicable)
3. Whether the conduction channel, gap(s) and critical isthmus are identified (Y/N) (as applicable)
4. Whether the mapping density at the areas of interests (e.g. slow conduction zones) is adequate, as assessed by the investigator (Y/N)

In addition, whether the OPTRELL™ catheter was used to pace for phrenic nerve stimulation or local pacing capture will be presented.

20.4.7 Analysis for Primary Endpoints

Primary Effectiveness Endpoint is defined as the completion of all pre-ablation mapping requirements and any clinically indicated mapping with the OPTRELL™ catheter without resort to non-study mapping catheter(s).

The primary effectiveness endpoint (success/failure) will be summarized using categorical summaries for the PP Analysis Set.

The number of subjects who started the pre-ablation mapping procedures with the OPTRELL™ catheter will be summarized overall, per chamber and by arrhythmia subgroup. The proportion of subjects who meet the requirements for success in the primary effectiveness endpoint will be summarized per chamber and overall.

A listing of the primary effectiveness endpoint will be provided.

Primary Safety Endpoint is defined as the incidence of serious adverse events related to the OPTRELL™ catheter within 7 days of index procedure. An SAE will be counted as related to the OPTRELL™ catheter if the relationship to a study catheter is anything other than 'Not Related'.

The number of subjects with SAEs related to the study catheter will be summarized in the Safety Analysis Set overall, by chamber and by each arrhythmia subgroup by Preferred Term and level of relationship. All tables will present summaries both by subject and by event.

If a subject has multiple occurrences of an event within a level of summarization, then for the by-subject summaries only a single occurrence will be counted at each level of summarization at the highest level of severity/relationship; for the by-event summary each event will be counted.

Device related SAEs will be defined and summarized similarly. All SAEs will be listed by System Organ Class and Preferred Term, severity, causality (defined as possible, probable or having a causal relationship to the device and/or procedure), anticipation and outcome.

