10.3 Subject Disposition

- **Enrolled Subjects:** Patients who sign the ICF.
- **Excluded Subjects:** Subjects who are enrolled but never undergo insertion of the study catheter. Excluded subjects will be subjected to safety event reporting between ICF signature and date of exclusion. Subjects who signed the ICF but are found to be ineligible prior to insertion of the catheter are also considered as excluded.
- **Discontinued Subjects:** Enrolled subjects who have the study catheter inserted but no mapping points are taken with it. Discontinued subjects will remain in follow-up for 7 days for safety evaluation.

- **Lost to Follow-up Subjects:** Enrolled subjects of which contact is lost after most recent visit (despite 3 documented attempts to contact the subject).
- **Withdrawn / Early Termination Subjects:** Subjects who withdraw consent for study participation or are withdrawn by the investigator, are terminated from the study prior to completion of all follow-up visits.
- **Completed Subjects:** Enrolled subjects who have not been excluded, discontinued, withdrawn, terminated early, or lost-to-follow-up from the study prior to the final study visit.

11. Responsibilities

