14.2.2 Study Procedure

Subjects will arrive to the electrophysiology laboratory for their ablation procedure and will undergo preparation for the procedure per the hospital's standard protocol (discretion of investigator)

Overall Use of the Investigational Device

During study procedures, investigators will use the OPTRELL™ catheter instead of the institution's standard diagnostic catheter choice (e.g. LASSO® catheter or PENTARAY® catheter) for the study qualifying arrhythmia. **Any use of a non-investigational mapping catheter will result in failure of the primary effectiveness endpoint.**

Investigators should use the CARTO® 3 system to “bookmark” instances of abnormal study catheter “noise,” arrhythmias initiated by study catheter manipulation (e.g. PVCs). This will allow for analysis of the data.

Pre-Ablation Mapping Requirements

The physician is REQUIRED to map the chamber(s) of interest with the OPTRELL™ catheter prior to a standard of care ablation procedure.

Pre-ablation mapping is considered complete when ALL of the following are accomplished, as applicable:

1. the entire chamber(s) and areas associated with the targeted arrhythmia(s) are completely mapped using fast anatomical mapping (FAM)
2. Substrate or previous lesion line associated with the arrhythmia(s) is mapped
 - a. Substrate Voltage mapping recommended for **re-do AF, PsAF** and **VT** procedures
 - b. Local activation mapping recommended for **complex AT** and **VT** procedures
3. Conduction channel, gap(s) and critical isthmus are identified (as applicable)
4. Mapping density at the areas of interests (e.g. slow conduction zones) is adequate, as assessed by the investigator

Standard of Care Ablation Procedure

Treatment of study arrhythmias will be per institution's standard of care (SOC).

Post-SOC Ablation Procedure Mapping

If additional mapping is clinically indicated, the OPTRELL™ catheter is required to be used.

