14.2.4 Data Collection during Study Ablation Procedure

Procedural parameters collected during the procedure include but are not limited to:

- Pre-ablation mapping:
 - o Pre-ablation mapping duration with the OPTRELL™ catheter (i.e. time between first and last mapping point prior to first ablation point) by chamber.
 - o Mapping algorithms used (e.g. voltage map, LAT, etc.)
 - o CARTO® 3 modules used
 - o Types and numbers of areas of interest captured with the OPTRELL™ catheter (e.g. PV triggers, previous PVI lesion gaps, ventricular scar slow conduction zone, critical isthmus for atypical flutter, etc.) in pre-ablation mapping
 - o Mapping density
- Total procedure time

Following each procedure, physician feedback on the primary and secondary (if applicable) OPTRELL™ catheter used will be collected, using a 7-point Likert-scale survey; it will include feedback on maneuverability and handling, pacing, unipolar and/or bipolar signal quality, workflow, visualization, and catheter interactions. The survey will be entered into the eCRF for analysis.

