20.4.8 Analyses of Secondary and Additional Endpoints

Secondary Safety Endpoints will be analyzed using the Safety Analysis Set:

- All Serious Adverse Events
- All non-serious Adverse Events related to the OPTRELL™ catheter during the 7-day follow-up period

The number of subjects experiencing adverse events and the number of adverse events will be summarized in the Safety Analysis Set overall, per chamber and by each arrhythmia subgroup using categorical summaries similar to the primary safety endpoint.

A listing of device deficiencies including the category and timing of the device deficiency will also be provided. Each deficiency will indicate whether it resulted in an adverse event.

The below endpoints will be analyzed using the PP Analysis Set:

- Physician feedback on deployment, maneuverability, and signal quality acquired with the OPTRELL™ Catheter for mapping in the atria and ventricles.
A post-procedure survey of 11 questions, each with individual sub-questions will be administered. Each question/sub-question will be answered by the physician using a Likert scale of 1 to 7 (1=poor and 7=excellent) and will be summarized. The summary results of each question will be presented overall, by catheter configuration, per chamber and for each arrhythmia subgroup using continuous summaries. A 12th question will solicit any additional feedback from the physician in a free text field. A by subject listing including all feedback results will be provided.
- Procedural parameters will be analyzed by heart chamber, by catheter configuration and by arrhythmia subgroup.
 - Pre-ablation mapping duration with the OPTRELL™ catheter (i.e. time between first and last mapping point prior to first ablation point, as measured on CARTO®) and total procedure time, will be analyzed using continuous summaries of subjects where mapping with the study device is initiated.
 - Mapping density adequacy with the OPTRELL™ catheter (as assessed by investigator) will be presented with categorical summaries.
 - Mapping algorithms used with the OPTRELL™ catheter (i.e. voltage map and/or LAT.) will be presented with categorical summaries.
 - CARTO® 3 modules used with the OPTRELL™ catheter will be presented with categorical summaries.

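### Primary effectiveness is reported only where mapping was initiated, so a subject with the catheter inserted, never mapped and switched to another catheter is a protocol-defined failure missing from the proportion

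*Combined protocol and SAP*

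**What the plan says.** Section 20.4.7 defines primary effectiveness as finishing all required and clinically indicated mapping with the study catheter and without another mapping catheter. It names one population: "The primary effectiveness endpoint (success/failure) will be summarized using categorical summaries for the PP Analysis Set". Section 20.3 builds that set from subjects who meet the eligibility criteria and "in whom mapping procedures with the study catheter for the study arrhythmia are initiated". The Safety Analysis Set, in the same section, is everyone who had the study catheter inserted.

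Section 10.3 has a category, Discontinued, for this group: "Enrolled subjects who have the study catheter inserted but no mapping points are taken with it". These subjects stay in 7-day safety follow-up.

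Section 14.2.2, like the protocol summary, gives the failure rule: "Any use of a non-investigational mapping catheter will result in failure of the primary effectiveness endpoint". It sets no condition that mapping with the study catheter had started.

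The physician survey follows the same population. Section 20.4.8 introduces it with "The below endpoints will be analyzed using the PP Analysis Set", whereas Section 14.2.4 says: "Following each procedure, physician feedback on the primary and secondary (if applicable) OPTRELL™ catheter used will be collected".

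Section 20.4.3 covers disposition: "Subject disposition will be summarized and listed for the subject categories defined in protocol section 10.3 for all subjects".

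**The concern.** The failure rule and the analysis population do not cover the same subjects. If the study catheter is inserted, produces no points and is replaced by another mapping catheter, Section 14.2.2 scores a failure. Section 20.4.7 then computes the success proportion on a set that, read naturally, does not contain that subject.

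A primary objective is feasibility of mapping, in a first-in-human study run before CE-mark registration. Obtaining no points after insertion can be the plainest form of infeasibility, and it is the outcome the denominator removes. Because no test is planned, the descriptive proportion is the whole primary effectiveness result, so its denominator should match its own failure rule.

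Two related gaps follow. The plan does not define initiated, so it is unclear whether an attempted map with no points enters the PP set. The survey summary also leaves out ratings from procedures in which no study catheter began mapping, although deployment is one of the things being rated. If a second study catheter does map, the subject stays in the PP set and both catheters are rated.

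**Working it through.** The plan has no figure to reproduce. Section 20.2 bases the sample size on earlier experience, and Section 20.1 plans no formal inference. The only check available is the split: about 20 atrial + 10 ventricular = 30, which agrees.

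**Tracing one subject.** Catheter inserted, mapping never begun, another mapping catheter used:

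| Section | Consequence |
|---|---|
| 10.3 | Discontinued |
| 20.3, Safety Analysis Set | Included (inserted) |
| 20.3, PP set | Not included (mapping not initiated) |
| 14.2.2 | Failure of primary effectiveness |
| 20.4.7 | Not in the reported proportion |

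Section 10.2 provides for replacement only when ineligibility is found before insertion, so the plan does not provide for replacing this subject.

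**Direction.** An unmapped subject has not completed mapping with the study catheter and so cannot be a success under Section 20.4.7, whether switched or not. Removing non-successes from the denominator can only raise the proportion or, if everyone else also failed, leave it unchanged.

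**Size.** Let N be the number inserted, k the number inserted but unmapped, and f the failures after mapping began.

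- PP proportion = (N − k − f)/(N − k)
- All-inserted proportion = (N − k − f)/N

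N = 30, 20 and 10 come from Section 20.2, taking all planned subjects as eligible and inserted. The documents give neither k nor f, so both are assumed. Intervals are exact (Clopper-Pearson) two-sided 95%, the level in Section 20.1.

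Overall, N = 30, f = 0:

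| k | PP set | All inserted |
|---|---|---|
| 0 | 30/30 = 100% (88.4–100) | 30/30 = 100% (88.4–100) |
| 1 | 29/29 = 100% (88.1–100) | 29/30 = 96.7% (82.8–99.9) |
| 2 | 28/28 = 100% (87.7–100) | 28/30 = 93.3% (77.9–99.2) |
| 3 | 27/27 = 100% (87.2–100) | 27/30 = 90.0% (73.5–97.9) |

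With f = 0 the gap is k/N, or 1/30 = 3.3 points per case. With one further failure after mapping began (f = 1), k = 1, 2, 3 give 28/29 = 96.6% against 28/30 = 93.3%, 27/28 = 96.4% against 27/30 = 90.0%, and 26/27 = 96.3% against 26/30 = 86.7%.

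By chamber, k = 1, f = 0:

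| Chamber | PP set | All inserted |
|---|---|---|
| Ventricular, N = 10 | 9/9 = 100% (66.4–100) | 9/10 = 90.0% (55.5–99.7) |
| Atrial, N = 20 | 19/19 = 100% (82.4–100) | 19/20 = 95.0% (75.1–99.9) |

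**Chance that it arises.** If each subject has probability p of being inserted but unmapped, the chance of at least one in 30 is 1 − (1 − p)^30. For assumed p of 1%, 2%, 5% and 10% this is 26.0%, 45.5%, 78.5% and 95.8%.

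**The eligibility criterion.** This is a separate PP exclusion and can act the other way. With k = 0, one mapped failure and one ineligible subject mapped successfully, all inserted gives 29/30 = 96.7% and PP gives 28/29 = 96.6%, a difference of about 0.1 point.

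**The case against.** The best reply is that Sections 10.3 and 20.3 use different terms, points taken and mapping initiated, and never equate them. If an attempt counts as initiation, a subject in whom mapping was tried without a point is in the PP set and is scored a failure. That stands as an ambiguity and is why a definition is needed. It does not help a subject in whom mapping never began.

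Second, the failure rule reaches only subjects who were switched; an abort with no other mapping catheter does not trigger it. This is correct, but that subject still fails the completion requirement, so counting the case as not successful follows from the endpoint definition and needs no extra data.

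Third, the cases are not hidden. Section 20.4.3 tabulates disposition and summarises premature discontinuation by primary reason. Section 20.4.7 reports how many started mapping and promises an endpoint listing, although it does not state the listing's population. Section 20.4.8 lists device deficiencies. A careful reader could probably rebuild the all-inserted rate, but none of these outputs applies the failure rule to the headline proportion.

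Fourth, the study has no test or threshold, and Section 20.2 disclaims effectiveness claims. Section 20.4.7 plans counts and percentages and does not commit to an interval, so the intervals above are illustrative. Some aborts may not be device-caused, since the documents give no reasons for discontinuation. All of this limits the consequence.

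The survey point is weaker. Section 14.2.4 governs collection, not analysis, and many of its topics presuppose mapping. It is secondary, and the main conclusion does not depend on it.

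**Conclusion.** The concern holds. Read together, Sections 10.3, 14.2.2, 20.3 and 20.4.7 classify a switched subject in whom mapping never began as a failure and leave that failure out of the only planned effectiveness proportion. No effectiveness summary on all inserted subjects is planned.

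The bias runs in the favourable direction. Its size depends entirely on k: zero if no such case occurs, a few points overall for one or two cases, and 10 points in the ventricular group for a single case. These figures rest on assumed k and f and on 30 eligible subjects actually having the catheter inserted. Section 8.1 sets 30 enrolled and Section 10.3 counts enrolment from consent, so fewer may reach insertion. No error rate or decision rule is affected. The point should be fixed because it concerns a primary endpoint and costs little to correct.

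**What to change.** - **Section 20.4.7:** report primary effectiveness on the Safety Analysis Set, overall and per chamber. Count inserted-but-unmapped subjects as not successful. List the reason for each so that aborts not caused by the device can be seen, and flag any inserted subject later found ineligible. Keep the PP proportion as supportive.
- **Section 20.3:** state whether an attempted map with no points counts as initiated.
- **Section 20.4.8:** summarise the physician survey for all subjects with the study catheter inserted and a survey completed.

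The cost is SAP wording. The analysis set already exists, and insertion and mapping status are needed for disposition anyway; no visit, subject or procedure is added. The reported rate may be slightly less favourable and may include some aborts unrelated to the device and some ineligible subjects. The listing and the supportive PP result show how many.
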